Length of Study	11 years (1 year enrollment plus 10 years follow-up): follow-up visits at 6 to 12 weeks, at 6 months, and thereafter at 1, 2, 3, 4 (optional), 5, and 10 year (optional) years post hospital discharge.
Materials and Methods	Case report forms will be completed either in-office or hospital at Pre-op, Surgery, Discharge, and at the 6 to 12 weeks, at 6 months and thereafter at 1, 2, 3,4 (optional)5 and 10 year (optional) post-operation intervals.
Data Collection	Paper/Electronic
Statistical Reporting	Data collected will be summarized and reported to each participating investigator. Statistical analysis will be conducted by Zimmer Biomet or its designee. Survivorship will be evaluated using Kaplan-Meier.
Scores/Performance Assessments	Constant-Murley, Oxford Shoulder Score, EuroQol (EQ-5D), Revisions, Adverse Events, Radiographic Assessment.
Standards	
The PMCF is compliant with the below:
 
• ISO 14155: 2020 - Clinical investigation of medical devices for human subjects - Good clinical practice.• The Declaration of Helsinki (DoH) – Ethical principles for medical research involving human subjects.• European Regulation (EU) 2017/745.

ZIMMER BIOMET

Study Funding	Funding for this clinical study is made available by Zimmer Biomet to support clinical data collection, IRB/EC review fees and other expenses associated with the conduct and execution of this study protocol as outlined in the fully executed Clinical Trial Agreement.
---------------	--

2 STATISTICAL ANALYSIS PLAN

2.1 Sample Size

The primary endpoint of this study is the performance of the Anatomical Shoulder™ Fracture System, which is assessed by the Constant and Murley Score (CM) at five years.

The historical CM score of patients treated with similar implants was calculated as an average from four published study results. This historical CM consists of the resulting average (53.25) and its 95% confidence interval (± 4.38).

A claim of non-inferiority to the historical value will be made if the CM obtained in the experimental group is greater than the historical CM lower 95% confidence limit at 48.87. Thus, the null hypothesis of non-inferiority will be rejected if the lower 95% confidence limit of the CM of the experimental group is not greater than 48.87.

A sample size of 37 achieves 80% power to detect non-inferiority using a one-sided t-test when the margin of non-inferiority is -4.38 to the historical CM mean and the true difference between the CM of the AS Fracture Prosthesis and the historical CM is 3.0.

The data are drawn from a single population with a standard deviation of 17.6.

The significance level (alpha) of the test is 0.05.

Fifty-two patients enrolled in the study allow for a yearly attrition rate of 5.8% over the estimated five-year period.

Calculations have been performed with PASS 2011 (NCSS, LLC. Kaysville, Utah)

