2.2 Statistical Analysis

Data collected in the study will be summarized descriptively. Descriptive summaries will be the basis of study reports to participants, as well as to generate an overall summary of the clinical performance of the various implants captured within the database and may be used for reports and to support presentations and publications as needed.

Summaries will routinely describe categorical data as counts and percentages, and ninety-five percent confidence limits will be generally used to assess differences between different implant configurations. Routine summaries describing continuous data will be in the form of means, medians, standard deviations, minima, and maxima, and ninety-five percent confidence intervals will be used to contrast differences.

Routine summaries of implant survival, return to function, etc. (e.g. time to event) will generally be described via the Kaplan-Meier method and these will generally be accompanied with the corresponding crude rates (expressed as percentages). Routine summaries of complication data will be in the form of frequencies and percentages. Summaries may be further generated for strata within the study population, (e.g. males and females, at different cut-points in the body mass index continuum, etc.). Patient confidentiality will be protected at all times, and patient identifiers will not be included in study summaries.

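### The plan's only non-inferiority rule is stated in two ways that disagree, names non-inferiority as the null, and leaves the sidedness of the confidence limit open

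*Combined protocol and SAP*

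**What the plan says.** Everything on this point is in section 2.1 (Sample Size). The primary endpoint is performance, "assessed by the Constant and Murley Score (CM) at five years". The benchmark comes from four published results: "This historical CM consists of the resulting average (53.25) and its 95% confidence interval", with a half-width of 4.38, so its lower end is 53.25 − 4.38 = 48.87.

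Two consecutive sentences then give the decision rule:

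- **Claim sentence:** a "claim of non-inferiority to the historical value will be made if the CM obtained in the experimental group is greater than" the historical lower limit of 48.87.
- **Rejection sentence**, which opens with *Thus* and continues: "null hypothesis of non-inferiority will be rejected if the lower 95% confidence limit of the CM of the experimental group is not greater", with 48.87 again the cut-off.

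The next paragraph describes the test behind the sample size: "A sample size of 37 achieves 80% power to detect non-inferiority using a one-sided t-test", with a margin of −4.38, a true difference of 3.0 and an SD of 17.6. "The significance level (alpha) of the test is 0.05".

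Section 2.2 (Statistical Analysis) does not restate the primary rule. It covers descriptive summaries and says that "ninety-five percent confidence intervals will be used to contrast differences", without giving sidedness.

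**The concern.** There are three defects in the two sentences.

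1. **Two criteria.** The only confidence limit in the claim sentence belongs to the historical value; the study group's CM enters as a bare result. The rejection sentence compares the study group's own lower limit with the same cut-off. *Thus* presents the second as following from the first, but it does not: a mean modestly above 48.87 satisfies one and fails the other.
2. **Null and alternative reversed.** A test designed to detect non-inferiority has H0: mean CM ≤ 48.87, with non-inferiority as the alternative. The rejection sentence calls non-inferiority the null, so a result that merely fails to show it would be reported as having rejected it.
3. **Sidedness not stated.** Just before, the lower 95% limit of the historical CM means the lower end of a ± interval, which is two-sided. The sample size is for a one-sided test at 0.05. The rule does not say which kind of limit applies to the study group.

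This is the only formal claim rule in the plan. If it can be read in more than one way, the primary conclusion can depend on which sentence is applied once the five-year data are known.

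**Working it through.** **Inputs (all from section 2.1).** Historical mean 53.25; cut-off 48.87; margin 4.38; assumed true difference +3.0, so a true mean of 56.25; SD 17.6; 37 evaluable patients; one-sided alpha 0.05; 52 enrolled with 5.8% yearly attrition.

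**Step 1: reproduce the plan's sample size.** For a one-sample t-test against 48.87, the distance to detect is 4.38 + 3.0 = 7.38.

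- SE = 17.6/√37 = 2.893.
- Noncentrality = 7.38/2.893 = 2.55, with 36 degrees of freedom.
- At one-sided 0.05 the critical value is t(0.95, 36) = 1.688, and noncentral-t power is 80.4%. The smallest n reaching 80% is 37.

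The stated sample size is therefore correct for a one-sided test at 0.05, which corresponds to a one-sided 95% lower limit.

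**Step 2: observed mean needed under each reading, if the sample SD is 17.6.**

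- Claim sentence alone: above 48.87.
- Rejection sentence, one-sided limit: 48.87 + 1.688 × 2.893 = 53.75.
- Rejection sentence, lower end of a two-sided interval: t(0.975, 36) = 2.028, so 48.87 + 2.028 × 2.893 = 54.74.

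Both thresholds for the limit lie above the historical mean of 53.25. A study that observed exactly 53.25 would earn the claim under the first sentence and fail it under the second.

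**Step 3: probability of a claim at n = 37.** The bare-mean column is Φ((true mean − 48.87)/2.893); the others use the noncentral t distribution.

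| True mean (difference from 53.25) | Bare mean > 48.87 | One-sided 95% limit > 48.87 | Two-sided 95% lower end > 48.87 |
|---|---|---|---|
| 48.87 (−4.38) | 0.500 | 0.050 | 0.025 |
| 53.25 (0) | 0.935 | 0.437 | 0.313 |
| 56.25 (+3) | 0.995 | 0.804 | 0.699 |

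**Step 4: how often the two sentences disagree.** Passing the limit rule implies passing the bare-mean rule, so the probability of disagreement is the difference between columns.

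- One-sided limit: 0.935 − 0.437 = 0.498 at zero difference; 0.995 − 0.804 = 0.190 at +3 (from unrounded values).
- Two-sided lower end: 0.935 − 0.313 = 0.622 at zero difference; 0.295 at +3 (from unrounded values).

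A simulation of 400,000 trials per scenario, with the sample SD free to vary, gave 0.499 and 0.190, and 0.623 and 0.295.

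**Step 5: effect of the reversed null.** At zero true difference the one-sided rule fails with probability 1 − 0.437 = 0.563. A device equal to the historical mean would more often than not be reported as having non-inferiority rejected, although its true mean lies inside the margin.

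**Step 6: sample size if the limit is two-sided.** The smallest n for 80% power at +3 is 47. The planned attrition leaves 52 × (1 − 5 × 0.058) = 36.9 patients, or 52 × 0.942⁵ = 38.6 if compounded. Having 47 evaluable would need 47/0.942⁵ = 63.4, so 64 enrolled, or 47/0.71 = 66.2, so 67.

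**The case against.** The best defence is that the two sentences are meant to be read together. The claim sentence names the benchmark, and the sentence beginning *Thus* says how to compare the study CM with it. The next paragraph specifies a one-sided t-test, followed by alpha 0.05, and nobody running that test would make a claim on a bare mean. On this reading the 50% false-claim figure and the disagreement probabilities describe an unlikely application of the plan.

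Sidedness is also largely answered by inference, because the stated test corresponds to a one-sided 95% limit and reproduces n = 37. The ± 4.38 interval describes the benchmark, not the study test, and the intervals in section 2.2 serve descriptive summaries. The reversed null leaves the cut-off unchanged and works against the sponsor's claim, so it does not inflate false claims. Finally, this is a single-arm post-market study whose stated objective is to obtain outcome data.

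Much of this is fair. The one-sided reading is the likely intention, the 50% figure is a worst case, and the sidedness point is a clarification more than an error. But the claim sentence is the only one that says when a claim is made; the other says only when something is rejected. To reach a valid rule the reader must set aside the wording of one sentence and reverse the hypothesis in the other. The sidedness appears in the sample-size justification and not in the rule. Nothing elsewhere in the document restates the rule, and the plan does make a formal non-inferiority claim whatever its descriptive objective.

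**Conclusion.** The concern holds: the rule is wrong as written and must be corrected. The sample size is not in question, since n = 37 with 80.4% power is right for a one-sided 95% limit.

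At n = 37, with a sample SD of 17.6, observed means between 48.87 and about 53.75 satisfy the claim sentence and fail the rejection sentence read one-sided. Means between about 53.75 and 54.74 pass or fail the latter according to the unstated sidedness. The claim sentence applied literally and alone carries a 50% false-claim probability at a true mean of 48.87, against a stated 5%.

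These results assume normal-theory inference for the mean and exactly 37 evaluable patients; the probabilities take 17.6 as the true SD. The 50% figure and the disagreement probabilities depend on applying the claim sentence literally. The 69.9% power and the need for 47 patients apply only if the limit is meant to be two-sided. The reversed null depends on none of these assumptions.

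**What to change.** Replace both sentences in section 2.1 with one rule, for example:

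> H0: mean five-year CM ≤ 48.87; H1: mean five-year CM > 48.87. Non-inferiority is claimed only if the one-sided 95% lower confidence limit of the mean five-year CM exceeds 48.87. Otherwise no claim is made, and failure to reject H0 does not by itself show inferiority.

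Repeat the rule, or refer to it, in section 2.2 so that the analysis section contains the primary test. Make the change before the five-year analysis.

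With the limit declared one-sided, the cost is wording only: sample size, alpha, power and data collection stay as they are. One-sided is a choice, and the sponsor should confirm it. If the lower end of a two-sided 95% interval is intended, either restate power as 69.9% or raise the evaluable sample to 47, which at the plan's attrition means about 64 to 67 enrolled instead of 52.

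### The primary test gives no role to Constant-Murley scores before year five, although 13 to 15 of 52 shoulders are expected to lack a year-five value; if loss follows recorded scores, the result is biased

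*Combined protocol and SAP*

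**What the plan says.** Section 2.1 defines the primary endpoint as device performance, "which is assessed by the Constant and Murley Score (CM) at five years". The only formal test in the document is in the sample-size text: "A sample size of 37 achieves 80% power to detect non-inferiority using a one-sided t-test". Non-inferiority is claimed if the lower 95% confidence limit exceeds 48.87. Loss is handled through enrolment alone: "Fifty-two patients enrolled in the study allow for a yearly attrition rate of 5.8% over the estimated five-year period".

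The synopsis (Materials and Methods) says "Case report forms will be completed either in-office or hospital at Pre-op, Surgery, Discharge, and at the 6 to 12 weeks, at 6 months", then at 1, 2, 3, 4 (optional), 5 and 10 (optional) years. The scores listed are "Constant-Murley, Oxford Shoulder Score, EuroQol (EQ-5D), Revisions, Adverse Events, Radiographic Assessment". No table assigns scores to visits.

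Section 2.2 is descriptive. It names no primary model, no analysis set for the non-inferiority claim and no method for missing CM.

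**The concern.** The study has one arm and compares its mean with a fixed number, so no control group shares the effect of dropout and cancels it. If patients with poor shoulders leave more often, the mean of those who stay is too high, and the error favours the device. The patients who leave will often have CM scores at 1, 2 or 3 years that carry information about their year-five result. A t-test on year-five values alone gives those scores no weight. At stake are the 5% error rate of the plan's only formal claim and, to a smaller degree, its power, which has no reserve.

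**Working it through.** **Inputs from section 2.1.** Historical mean 53.25, margin 4.38 (threshold 48.87), assumed true difference +3.0, SD 17.6, one-sided alpha 0.05, 37 evaluable, 52 enrolled, 5.8% loss a year for five years.

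**Not in the documents, so assumed.** The correlation ρ between an earlier CM and the year-five CM (0.3 to 0.75), and the way in which patients are lost.

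**1. The plan's own figure.** Distance from threshold = 4.38 + 3.0 = 7.38. One-sample, one-sided t-test with noncentrality 7.38/17.6 × √n: n = 37 gives 80.4% power and n = 36 gives 79.4%. The stated 37 reproduces exactly.

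**2. Expected missing values.** Linear loss: 52 × (1 − 5 × 0.058) = 36.9, so about 15 missing. Compound loss: 52 × 0.942⁵ = 38.6, so about 13 missing. The linear figure matches the plan's 37.

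**3. Loss unrelated to outcome.** The year-five-only SE is 17.6/√37 = 2.89. With an earlier CM on all 52 shoulders, the likelihood estimate has

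Var = 17.6² × [(1 − ρ²)/37 + ρ²/52].

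| ρ | SE | Reduction | Effective n | Power |
|---|---|---|---|---|
| 0.3 | 2.86 | 1.3% | 38.0 | 81% |
| 0.5 | 2.79 | 3.7% | 39.9 | 83% |
| 0.6 | 2.74 | 5.3% | 41.3 | 84% |
| 0.75 | 2.65 | 8.5% | 44.2 | 86% |

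This is the best case. If half of the 15 losses are deaths and are left out, 52 becomes 44.5. Effective n is then 39.4 (ρ = 0.6) to 40.9 (ρ = 0.75), and power 82.6% to about 84%. If the losses are also spread evenly over the five years, many patients leave before year 3. Taking adjacent-visit correlations of √ρ among years 1, 2 and 3, effective n is 38.5 to 39.6 and power about 82% to 83%; at ρ = 0.3 power is 80.7%. With no loss the gain is zero, since both SEs are 17.6/√52 = 2.44.

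**4. Loss that depends on a recorded CM.** Assumption: the odds of loss double per SD lower earlier score, with 71% retained. Simulation (20,000 trials per case, one earlier score) gives a year-five-only bias close to 3.2ρ points. The false-claim rate at a true mean of 48.87 is then roughly P(Z > 1.645 − bias/2.89). For ρ = 0.6, 1.645 − 1.9/2.89 = 0.98, or 16%; the simulated value is 17%.

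| ρ | Bias, year five only | False claims | Bias, earlier CM used | False claims |
|---|---|---|---|---|
| 0.3 | +1.0 | 9% | 0.0 | 5% |
| 0.5 | +1.6 | 14% | 0.0 | 5% |
| 0.6 | +2.0 | 17% | 0.0 | 5% |
| 0.75 | +2.4 | 21% | 0.0 | 5% |

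Two simulations with CM at 1, 2, 3 and 5 years, and loss depending on the last recorded score, agree. One gave a bias of 1.2 to 2.8 points and 11-21% false claims (ρ 0.4 to 0.75), against 4-6% for the repeated-measures estimate. The other gave 2.1 to 2.9 points and 17-25% (ρ 0.6 to 0.75, 35 to 37 shoulders left), against 5-6%.

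**5. Loss that depends on the unseen year-five score.** With the same doubling of odds, the year-five-only bias is +3.2 to +3.3. Using earlier CM, it is +3.0 at ρ = 0.3 and falls to +1.3 at ρ = 0.8. The bias is reduced, not removed.

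**The case against.** The sample-size sentence contains no error, and a t-test on year-five values is a simple, valid test of the stated endpoint if loss is unrelated to outcome. In a small, non-comparative post-market study that is otherwise descriptive, it can be defended as a choice. That stands.

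Three stronger readings are tempting, and the documents do not support them:

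- A reader might infer that the plan discards CM data known to exist. It does not say so. Collection of CM at each visit is inferred from a general form schedule and a list of scores, and the t-test is named only in the sample-size section. The exact statement is that earlier CM has no role in the primary claim.
- A reader might infer that the primary estimate is biased whatever happens. The dropout mechanism is assumed. With loss unrelated to score the bias is zero, and if good scorers left more often it would work against the device.
- A reader might infer a large loss of precision. Against a fixed threshold, earlier scores add nothing for shoulders that have a year-five value. The gain comes only from dropouts and may be under one percentage point of power.

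Two practical objections also stand. An unstructured model on all six scheduled post-operative visits to year five has 6 × 7/2 = 21 covariance parameters, or 28 with optional year 4, which is heavy for 52 shoulders. Restricting the analysis to patients alive at year five would need vital status on those lost, which the documents do not mention.

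What does not stand is the view that this is only a missing detail. The plan budgets for about 29% loss and answers it with numbers enrolled, which protects power but not against bias.

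**Conclusion.** The point holds in a conditional form and is worth acting on. The case rests mainly on protecting the error rate. For loss driven by recorded scores, at the assumed strength, the year-five-only mean is about 1 to 3 points too high, and the false-claim rate is about 9-25% rather than 5%. Using earlier CM restores about 5%. For loss unrelated to outcome the t-test is sound, and the gain is from under one to about six points of power. For loss driven by unseen scores the improvement is partial. In none of these scenarios was the estimate using earlier CM more biased to a degree that matters.

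These sizes rest on an assumed correlation, an assumed dropout strength and the inference that CM is scored at years 1, 2 and 3. The sample size need not change.

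**What to change.** In sections 2.1 and 2.2:

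- State at which visits CM is scored.
- Make the primary estimate the year-five mean from a likelihood-based repeated-measures model, or from multiple imputation, using CM at 1, 2, 3 and 5 years. Four visits need 4 × 5/2 = 10 covariance parameters. Omit optional year 4 and name a simpler covariance as a fallback if the model does not converge.
- Compare its one-sided 95% lower limit with 48.87, and report the year-five-only t-test beside it.
- Add a sensitivity analysis for loss related to unseen scores.
- Where a death is recorded, do not project CM past it.

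The cost is SAP wording and a few lines of code, with no new visits if CM is already scored at those visits. The downside is that the primary number becomes model-based and assumes that loss depends on recorded scores. Settling this before analysis also prevents the method from being chosen after the data are seen.

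### Section 2.1 turns a missed confidence limit into a rejection of non-inferiority, an outcome that an implant equal to history would meet about 56% of the time with 37 evaluable shoulders

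*Combined protocol and SAP*

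**What the plan says.** All of this is in section 2.1 (Sample Size) of the combined protocol and SAP.

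- **Endpoint.** Performance is "assessed by the Constant and Murley Score (CM) at five years", in a single arm compared with a historical value.
- **Benchmark.** "The historical CM score of patients treated with similar implants was calculated as an average from four published study results". The average is 53.25, with a 95% confidence interval of plus or minus 4.38.
- **Threshold and margin.** The threshold is the "historical CM lower 95% confidence limit at 48.87". Equivalently, "the margin of non-inferiority is -4.38 to the historical CM mean".
- **Power.** "A sample size of 37 achieves 80% power to detect non-inferiority using a one-sided t-test", given that margin and given that "the true difference between the CM of the AS Fracture Prosthesis and the historical CM is 3.0". The SD is 17.6 and alpha is 0.05.
- **Enrolment.** 52 patients, to allow for 5.8% attrition a year over five years.
- **Decision rule.** One sentence allows the claim if the study's CM is above 48.87. The next names non-inferiority as the null hypothesis and says it is rejected if the lower 95% confidence limit is not above 48.87.

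The documents give no reason for the 3.0, no power at a true difference of zero, and no other account of how a missed limit is to be reported. Section 2.2 describes descriptive summaries only.

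**The concern.** In a non-inferiority test the null is that the mean is at or below the threshold, and the study tries to reject it. Failing to do so leaves the question open. Section 2.1 reverses this: non-inferiority is the null, and a lower limit that does not clear 48.87 rejects it. Taken literally, every study that is not a clear success becomes a finding against the implant.

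How much this matters depends on how often a satisfactory implant misses the limit. The 80% suggests a miss is uncommon, but that figure belongs to a true mean of 56.25 (53.25 + 3.0). The planned distance to the threshold is 7.38 points (4.38 + 3.0), not the 4.38 of the margin. If the implant only matches the implants it is compared with, misses are frequent, and the primary endpoint would be reported with a negative conclusion that the data do not support.

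**Working it through.** **Inputs (all from section 2.1).** Historical mean 53.25; threshold 48.87; margin 4.38; assumed true difference d = +3.0; SD 17.6; one-sided alpha 0.05; n = 37 evaluable, 52 enrolled.

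**Method.** One-sample, one-sided t-test by the noncentral t distribution, with df = n - 1 and noncentrality (4.38 + d) x sqrt(n) / 17.6. The critical t at df = 36 is 1.688.

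**Step 1: the plan's own figure.** With d = 3.0 and n = 37, noncentrality = 7.38 x 6.083 / 17.6 = 2.551 and power = 80.4%. At n = 36 power is 79.4%, so 37 is the smallest n that reaches 80%. The stated figure is reproduced. It is reproduced only with d counted in the implant's favour and alpha 0.05 one-sided; one-sided 0.025 gives 69.9% at n = 37.

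**Step 2: power at other true differences, n = 37.** At d = 0, noncentrality = 4.38 x 6.083 / 17.6 = 1.514.

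| True difference | Lower limit above 48.87 | Limit missed |
|---|---|---|
| +3.0 | 80.4% | 19.6% |
| +2.0 | 69.8% | 30.2% |
| +1.0 | 57.1% | 42.9% |
| 0 | 43.7% | 56.3% |
| -1.0 | 30.9% | 69.1% |

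**Step 3: dependence on the evaluable number, d = 0.** Attrition taken as a simple sum gives 52 x (1 - 5 x 0.058) = 36.9. Compounded, it gives 52 x 0.942^5 = 38.6. Power is 43.7% at n = 37, 44.5% at n = 38, 50.7% at n = 46 and 55.0% at n = 52.

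**Step 4: which null the calculation used.** If the true mean is exactly 48.87, the lower limit clears the threshold 5% of the time. The stated alpha of 0.05 is therefore the error rate for the null 'true mean at or below 48.87'. If non-inferiority were really the null, the written rule would reject it 56.3% of the time at a true mean of 53.25 and 95% of the time at the threshold itself. Neither is a 5% test, so the sentence contradicts the section's own alpha and power.

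**Step 5: what a miss looks like.** At the planned SD and n = 37 the limit clears 48.87 when the observed mean is at least 48.87 + 1.688 x 17.6 / 6.083 = 53.75. An observed mean of 53.25 gives a one-sided lower limit of 53.25 - 4.88 = 48.37 and an upper limit of 53.25 + 4.88 = 58.13. The rule as written rejects non-inferiority there, although the estimate equals the benchmark. For the one-sided upper limit to lie below 48.87, the observed mean must be under 48.87 - 4.88 = 43.99. A truly equal implant would produce that about 0.1% of the time (noncentral t, n = 37).

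**The case against.** The assumption is disclosed: the 3.0 stands in the same sentence as the 80%. Powering a non-inferiority test at a non-zero true difference is permissible when declared, and no number is wrong. 'Similar' describes the type of comparator and does not assert equal scores. The study is non-comparative surveillance, summarised mainly descriptively. All of this stands, and restating the power at zero difference would by itself be only a transparency request.

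Several stronger readings are tempting, and the documents do not support them.

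- *The sample size is wrong.* It is not; it reproduces exactly.
- *An advantage of 3.0 is unrealistic, or zero is the right planning value.* The four published results are not in the documents. One can say only that no rationale is given.
- *The study is more likely than not to miss its claim.* That needs true equality, an SD near 17.6 and at most 45 evaluable shoulders together. At n = 52 power is 55.0%; at n = 37 with an SD of 15 it is 53.9%.
- *The rule can be met only by outscoring history.* At n = 37 an observed SD below about 15.8 (4.38 x 6.083 / 1.688) lets a mean of 53.25 pass. At n = 52 the smallest passing mean is 52.96.

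The decision wording could also be read in other ways. Its first sentence alone suggests a point-estimate rule, but the next sentence and the t-test calculation rule that out. A lower limit from a two-sided 95% interval would give 31.3% power at zero difference. The stated n fits only the one-sided 95% limit, and the replacement text should say so.

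Finally, one may call the reversed null a slip that no analyst would apply. That may be so, but it is the only instruction the plan gives for a missed limit.

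**Conclusion.** The point holds for the decision sentence. Section 2.1 is wrong as written in treating a lower limit at or below 48.87 as rejection of non-inferiority. An implant equal to the historical mean would receive that report about 56% of the time at 37 evaluable shoulders, and 45% of the time (100% - 55.0%) if all 52 are evaluable. Even at the assumed +3.0 it would do so 19.6% of the time at n = 37. These figures rest on SD 17.6, a one-sided 0.05 test and the noncentral t.

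The 80% power is correct under its stated condition. Its dependence on an unexplained 3.0-point advantage is supporting context: it shows why a missed limit must not be read as evidence against the implant. It is not a separate error and gives no ground for calling the sample size miscalculated.

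**What to change.** In section 2.1, replace the sentence on rejecting the null hypothesis with:

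> H0: true mean CM <= 48.87. Non-inferiority is claimed if the one-sided 95% lower confidence limit exceeds 48.87. Otherwise the result is reported as inconclusive, as the mean with its confidence interval, unless the one-sided 95% upper limit is also below 48.87, in which case the implant is reported as inferior to the threshold.

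Next to the 80%, add that power at 37 evaluable shoulders is 44% if the true mean equals 53.25 (SD 17.6, one-sided 0.05), and give the reason for the 3.0 if there is one.

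**Cost.** No extra patients, visits or data. The stated power looks less favourable. The change goes beyond tidying, because it adds an inconclusive outcome and so alters what is reported after a missed limit. The condition for claiming non-inferiority stays the one that the sample size calculation already uses.
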